#### 12.4.4 Sensitivity analyses

- For patients who have a reinfection after 7 days but prior to Day 29 visit, such as at Day 15, the statistical method specified in [Section 12.4.2](#) will be performed by assigning treatment failure to these patients.
- The primary efficacy variable will be performed based on the FAS using the statistical method specified in [Section 12.4.2](#). Missing primary efficacy variable will be handled as follows:
  - Patients who received rescue medication for the treatment of *P. falciparum* malaria (except for the treatment of a new infection) will be considered treatment failures (from the day of rescue use onwards).
  - Patients who received other concomitant medication having an effect on malaria for reasons other than rescue therapy e.g. for the treatment of *P. vivax* [REDACTED]

(e.g., primaquine, certain antibiotics (sulfonamides, tetracycline, etc.)) will be considered in the analysis as if they had not taken the drug.

- Patients will be counted as failure if (a) they did not have a parasite count assessment at Day 29 unless these patients could be classified as cured based on absence of parasitemia at later time, or (b) they did not have valid PCR evaluations at baseline and Day 29 if parasitemia was present at Day 29.
- In addition, for the FAS, the proportion of patients with PCR-corrected ACPR at Day 29 and 95% CI by treatment group and the difference will be also estimated using the Kaplan-Meier method (Stepniewska and White 2006 and WHO 2015) which uses treatment failure as the event and treats missing data as censored instead of treatment failure. The PCR-corrected ACPR rate at Day 29 is estimated by the survival function at Day 29. Patients who had a new infection (i.e., reinfection) with *P. falciparum* or other species without *P. falciparum* recrudescence on or after Day 8 will be censored at the time of the first PCR that indicate the infection; patients who took antimalarial medications for reinfection or reasons other than rescue medication given for signs and symptoms of infection with *P. falciparum* or unsatisfactory therapeutic effect will be censored at the first time of such antimalarial medications; other patients without treatment failure will be censored at the time of the last parasitemia assessment. A two-sided 95% CI for the difference in proportion between the 2 treatment groups will be calculated based on the variance of individual proportion using the Greenwood formula.

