2.5.4 Sensitivity analyses

- The primary efficacy analysis will be repeated on the FAS using the statistical methods specified in [Section 2.5.2](#). Primary efficacy variable will be handled additionally for those patients who are excluded from the PPS as follows:
 - Presence of parasitaemia which cannot be determined to be recrudescence or new infection due to missing PCR data will be counted as non-responders (from the day of test)
 - Missing/undetermined responses at Day 29 due to missing blood smear data at the visit will be counted as non-responders unless there is a later blood smear test indicating no parasitemia.
 - Patients with new infection before Day 29 will be considered 1) not achieving PCR-corrected ACPR at Day 29 in one analysis and 2) and achieving PCR-corrected ACPR at Day 29 in another analysis
 - Patients who received non-study related anti-malarial medication without having reappearance of the parasites will be considered in the analysis as if they had not taken these drugs. This is because such cases will be very unlikely as administration of such medicines are expected only in case of the reappearance of the parasites. Note- Patients who take non-study anti-malarial medication due to repeated vomiting of study medication should be considered as treatment failure.

Note: These patients did not experience any treatment failure (ETF, LCF, or LPF). In case that non-PPS patients who experienced treatment failure, they will be included as non-responders if they received rescue medication for the treatment of *P. falciparum* malaria due to recrudescence or as responder for PCR corrected ACPR if they received rescue medication to treat a new infection on Day 29 visit.

- Patients who received non anti-malaria medication with potential anti-malarial activity without having reappearance of the parasites will be considered in the analysis as if they had not taken these drugs. This is because such medications will have minimal effect on efficacy.

- Although the objective of Run-in cohort is to investigate the food effect on bioavailability of KAF156 and lumefantrine, analyses related to primary and other secondary variables will be performed in Run-in cohort by treatment group, unless otherwise specified.

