2.5.4.1 Analysis of PCR-corrected ACPR rate using Kaplan-Meier method

For the FAS, the proportion of patients with PCR-corrected ACPR at Day 29 and 95% CI will be also estimated using the Kaplan-Meier method ([Stepniewska and White 2006](#) and [WHO 2015](#))

Event = PCR-corrected non-responder during the study (same as at Day 15, Day 43, see [Section 2.1](#)). The event time is the first time when the patient becomes a non-responder based on PCR-correction. If a patient parasite is not cleared at all, Day 7 is considered as the event time.

The PCR-corrected responder rate at Day 29 is estimated by the survivor function at Day 29 using the Kaplan-Meier method.

Rule for censoring:

The following censoring rules will be applied to the patients who were not non-responder

- Patients who had a new infection with *P. falciparum* or other species without *P. falciparum* recrudescence on or after Day 8 will be censored at the first time of the PCR that indicate the infection or blood smear with other species.
- Patients who received non-rescue antimalarial medication for other infections [REDACTED] will be censored at the first time of antimalarial medication.
- Patients who have parasites at Day 8 or later but cannot be determined as recrudescence or new infection due to missing PCR genotyping will be censored at the time of the first malaria blood film with presence of parasites on or after Day 8.
- Other patients not classified as non-responder will be censored at the time of last parasitemia assessment.

An asymptotic two-sided 95% CI for the difference in proportion of responders between two treatment groups will be calculated from the z-test statistic distribution based on the variance of individual proportion using the Greenwood formula.

The confidence interval will be constructed as: $(r_k - r_c) \pm Z_{\alpha/2} * SE_d$;

where,

r_k = Kaplan-Meier estimate for the treatment group at time t,

r_c = Kaplan-Meier estimate for the control group at time t,

$SE_d = \sqrt{(SE_k^2 + SE_c^2)}$,

SE_k = estimated standard error for the treatment group based on Greenwood's formula,

SE_c = estimated standard error for the control group based on Greenwood's formula,

$Z_{\alpha/2}$ = z-statistic = probit(1- α /2) from a normal distribution function, $\alpha = 0.05$.

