2.7.2.2 Analysis of uncorrected ACPR rate using Kaplan-Meier method

Analysis will be performed on the FAS and PPS.

If Cohort 2 does not stop early-

The proportion of patients with uncorrected ACPR at Day 29 and Day 43 and 95% CI will be estimated using the Kaplan-Meier method ([Stepniewska and White 2006](#) and [WHO 2015](#)) stratified by Cohort. For each cohort, an asymptotic two-sided 95% CI for the difference in proportion of responders between two treatment groups will be calculated from the z-test statistic distribution based on the variance of individual proportion using the Greenwood

formula (See [Section 2.5.4.1](#)). For pooled cohorts 1 and 2, an asymptotic two-sided 95% CI for the difference in proportion of responders between two treatment groups will be calculated.

If Cohort 2 stops early-

The proportion of patients with uncorrected ACPR at Day 29 and Day 43 and 95% CI will be estimated using the Kaplan-Meier method ([Stepniewska and White 2006](#) and [WHO 2015](#)) by Cohort except Cohort 1 along with an asymptotic two-sided 95% CI for the difference in proportion of responders between two treatment groups. For Cohort 1, an asymptotic two-sided 95% CI for each treatment group along with between treatment difference in proportion of responders will be calculated

Event = PCR-uncorrected non-responder during the study (same as at Day 15, Day 43, See [Section 2.1](#)). The event time is the first time when the patient becomes a non-responder without PCR-correction. If a patient parasite is not cleared at all, Day 7 is considered as the event time.

The uncorrected ACPR rate at Day 29 is estimated by the survivor function at Day 29.

Rule for censoring:

The following censoring rules will be applied to the patients who were not non-responders

- Patients who received non-rescue anti-malaria medication (i.e., receiving antimalaria treatment without reappearance of parasites) will be censored at the first time of anti-malaria medication.
- Other patients will be censored at the time of last parasitemia assessment.

Appendix Table 5-21 provides a comparison of treatment outcome assignments for both uncorrected and PCR-corrected ACPR in FAS and PPS for various specific scenarios.

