3.1.1 Primary endpoint(s)

The primary objective is to evaluate the efficacy of KAF156 combined with LUM-SDF by demonstrating non-inferiority to Coartem[®] in PCR corrected ACPR at Day 29 for treatment of uncomplicated malaria caused by *P. falciparum* in children 6 months to < 12 years old. The NI margin (Δ) has been set to 10%. There is no historical Coartem[®] trial that compared Coartem[®] with placebo in PCR corrected ACPR at Day 29 to justify the NI margin statistically. The 10% NI margin in PCR corrected ACPR at Day 29 is based on clinical judgement as a NI margin of 10% to 12.5% is commonly used in other infection diseases (e.g., FDA 2018 guidance for

Complicated Urinary Tract Infections, FDA 2020 guidance for Hospital-Acquired Bacterial Pneumonia and Ventilator-Associated Bacterial Pneumonia, EMA 2014 Addendum to the guideline on the evaluation of medicinal products indicated for treatment of bacterial infections, etc.).

The statistical null hypothesis is that the difference in PCR-corrected ACPR rate at Day 29 between KAF156 and LUM-SDF combination and Coartem[®] is at most -10% with the alternative hypothesis that it is greater than -10%. The non-inferiority of KAF156 and LUM-SDF combination in PCR corrected ACPR rate at Day 29 will be evaluated based on the per-protocol analysis set using Cohorts 1 and 2 pooled if Cohort 2 does not stop early or using Cohort 1 data alone if Cohort 2 stops early.

Cohort 2 does not stop early

The statistical hypothesis will be evaluated using the lower limit of 2-sided 95% confidence interval (CI) for the difference between two treatment groups using Cohorts 1 and 2 pooled based on Mantel-Haenszel estimate of the common risk difference stratified by cohort (see [SAS manual version 13.2 Pages 2681-2682, 2014](#)). If the lower confidence limit is greater than -10%, the null hypothesis will be rejected. That means the non-inferiority will be established at -10%.

[figure not shown]
Assuming that the true response rate in PCR corrected ACPR at Day 29 is 95% for both treatment groups, a sample size of 92 patients per group will have at least 87% power to reject the null hypothesis that the response rate for KAF156 and LUM-SDF combination is at least 10% lower than Coartem[®] at 1-sided alpha of 2.5% (nQuery 8.4 module PTE0-1/Two Group Test of non-inferiority in Proportions).

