5.7.3 Other secondary/exploratory analysis

Kaplan-Meier estimates

An estimate of the survival function in each treatment group will be constructed using Kaplan-Meier (product-limit) method as implemented in PROC LIFETEST with METHOD=KM option. The PROC LIFETEST statement will use the option CONFTYPE=LOGLOG.

Median survival for each treatment group will be obtained along with 95% confidence intervals calculated from PROC LIFETEST output using the method of [Brookmeyer and Crowley 1982](#). Kaplan-Meier estimates of the survivor function with 95% confidence intervals at specific time points will be summarized. The standard error of the Kaplan-Meier estimate will be calculated using Greenwood's formula [Collett 1994](#).

Difference in responder rates stratified by cohort using Mantel-Hanszel estimate

For PCR corrected and uncorrected ACPR rates, the between treatment difference will be evaluated using a Mantel-Haenszel estimate of the treatment difference in responder rates stratified by cohort using PROC FREQ with RISKDIFF(COMMON) option in the TABLES statement).

Difference in responder rates using the Wilson uncorrected method

For PCR corrected and uncorrected ACPR rates, the between treatment difference will be evaluated using a Wilson uncorrected method using PROC FREQ with RISKDIFF (CL=NEWCOMBE) option in the TABLES statement.

Difference in parasite clearance (fever clearance) rate using log-rank test

For parasite clearance and fever clearance rates, the between treatment difference will be evaluated using log-rank test using PROC LIFETEST with STRATA <treatment> and TEST <treatment> statements. For pooled time to event data from cohort 1 and 2, stratified log-rank test will be performed using GROUP = <cohort> option in STRATA statement.

Confidence interval for Post treatment max QTcF/QTcB increase from baseline

For maximum increase in QTcF/QTcB from baseline, 2-sided $100 \times (1 - \alpha) \%$ confidence intervals (CI) for the difference between the 2 treatment groups will be calculated using PROC TTEST by assuming normality of data.

Confidence interval for geometric mean ratio

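### The Kaplan-Meier ACPR difference uses a plain Greenwood z-interval with no rule for an arm without failures, so this supportive interval is unreliable in the small cohorts

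*SAP*

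**What the plan says.** SAP 2.5.4.1 sets the interval as the difference of the two Kaplan-Meier estimates plus or minus 1.96 times the root of the summed squared standard errors. Its wording is: "An asymptotic two-sided 95% CI for the difference in proportion of responders between two treatment groups will be calculated from the z-test statistic distribution". Protocol 12.4.4 has the same basis: "based on the variance of individual proportion using the Greenwood formula".

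SAP 2.7.2.2 carries the method to uncorrected ACPR with a reference back to 2.5.4.1: "For each cohort, an asymptotic two-sided 95% CI for the difference in proportion of responders between two treatment groups will be calculated". It also asks for an interval for Cohorts 1 and 2 pooled, without a formula. SAP 2.5.4 extends the efficacy analyses to the Run-in Cohort: "analyses related to primary and other secondary variables will be performed in Run-in cohort by treatment group".

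SAP 5.7.3 adds, for the survival curve of each arm: "The PROC LIFETEST statement will use the option CONFTYPE=LOGLOG". This does not govern the difference.

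For the binary ACPR difference by cohort, SAP 2.7.2.1 uses the Wilson uncorrected (Newcombe) method. Neither document says what to do with the Kaplan-Meier difference when an arm has no failures.

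**The concern.** Greenwood's variance is a sum over event times. An arm without events contributes an empty sum, so its rate is treated as known exactly, whether it holds 12 patients or 110. With a planned response of 95% and cohorts of about 70 and 40 per arm, fewer in the Run-in Cohort or a stopped Cohort 2, arms without failures are foreseeable.

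The Kaplan-Meier analysis is the one FAS analysis of the primary variable that censors a missing Day 29 result; the other FAS analyses score it as non-response unless a later smear is negative. Its use as a robustness check depends on a credible interval. As written, a report could show [0, 0] from this method beside a Wilson interval of about plus or minus 9 points for the same 40-per-arm cohort.

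**Working it through.** **Inputs.** 95% PCR-corrected response in both groups, 92 evaluable per group, one-sided 2.5% and a 10-point margin (SAP 3.1.1). Cohort 1 about 140 and Cohort 2 about 80 patients, randomized 1:1 (Protocol 3), so 70 and 40 per arm. Cohort 2 may stop at 24 or 48 patients (SAP 1.1), so 12 or 24 per arm. Run-in 12 per arm (SAP 1.1).

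**The plan's own figure.** SAP 3.1.1 states: "a sample size of 92 patients per group will have at least 87% power". The unpooled normal approximation gives Φ(0.10/√(2×0.95×0.05/92) − 1.96) = Φ(3.11 − 1.96) = 87.5%. The total is 184/0.84 = 219, stated as about 220. Both reproduce. The documents state no coverage or width for the Kaplan-Meier interval.

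**Mechanism.** Var(S) = S² Σ d/(r(r−d)) over event times. With no events the sum is empty and SE = 0, also under censoring: 40 patients with 6 censored and no event give S = 1, SE = 0. Without censoring before Day 29 the formula reduces to S(1−S)/n, so the interval equals the unpooled Wald interval. At S = 100% the log-log limits need log(−log 1) = log 0, which is undefined.

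**How often.** With q = 0.95^n, at least one arm has zero SE with probability 1 − (1−q)², and both arms with probability q².

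| n per arm | at least one arm SE = 0 | CI = [0, 0] |
|---|---|---|
| 12 | 78.9% | 29.2% |
| 24 | 49.9% | 8.5% |
| 40 | 24.1% | 1.7% |
| 70 | 5.4% | 0.1% |
| 110 | 0.7% | 0.0013% |

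At an assumed 98%, the middle column at 40 per arm is 69.3%. For uncorrected ACPR no rate is given; over an assumed 80-90% it is 0.03-2.9% at 40 per arm and at most 0.13% at 70.

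**Size for given data.** No failures in either arm: Greenwood [0, 0] at every n; Wilson ±24.3 points (12), ±8.8 (40), ±5.2 (70). One KAF156/LUM-SDF failure against none at 40 per arm: SE = √(0.975×0.025/40) = 2.47 points, so Greenwood gives −2.5 ± 4.8 = [−7.3, +2.3]. Wilson gives [−12.9, +6.5].

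**Coverage (exact binomial enumeration, no censoring).** At 95% in both arms: 97.9% (12), 98.2% (24), 95.7% (40), 93.7% (70), 95.5% (110). A [0, 0] interval counts as covering here only because the true difference is zero. Over assumed pairs of rates from 93% to 99%, the lowest coverage is 30%, 51%, 70% and 87% at 12, 24, 40 and 70 per arm (98% against 99%); Wilson stays at or above 96%.

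**Lower limit at a true −10 points.** For 85% against 95%, it lies above −10% in 4.7% of trials at 40 per arm, 3.6% at 70 and 3.1% at 110 (nominal 2.5%). Trials with no zero-failure arm supply 4.44 of 4.73 points, 3.61 of 3.62, and all 3.11. At these sizes it is therefore mainly ordinary skewness of the Wald interval, separate from the zero-variance defect.

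**The case against.** The strongest reply is that little depends on this interval. The non-inferiority test uses the PPS with the Mantel-Haenszel interval, or Wilson if Cohort 2 stops early; SAP 2.7.2 calls the secondary endpoints supportive and states no hypotheses for them. Wilson intervals by cohort and Clopper-Pearson intervals by arm are reported alongside, so a [0, 0] would be conspicuous. The explicit by-cohort text concerns uncorrected ACPR, where new infections also count as failures and empty arms are rarer. SAP 2.5.4.1, on PCR-corrected ACPR, does not itself split by cohort, and at the pooled size the defect is under 1%. All of this stands and limits the point.

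A reader might infer that the cohort-level error bars are wrong throughout. Coverage of 94-98% at the planning rate does not support that. A reader might also take the lower-limit error rates as the harm done by empty arms, or as a risk of falsely declaring non-inferiority. At 40 per arm and above they come mostly from trials without an empty arm, and no decision in the plan uses this limit.

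The reply does not remove the gap: the formula returns an impossible precision in a foreseeable case, and neither document says what to report then.

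**Conclusion.** The point holds as a defect of a supportive analysis. It matters most at 12 to 24 per arm, is material for PCR-corrected ACPR in a full Cohort 2, is occasional in Cohort 1 and negligible for the pooled cohorts. The mild anti-conservatism of the lower limit is a second, separate weakness, and the same replacement addresses it: Newcombe on the same data gives 1.3-2.5% over the two scenarios examined at 40 to 110 per arm (85% against 95%, and an assumed 88% against 98%). The primary conclusion is not touched.

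The figures assume no censoring before Day 29. The documents give 95% only for PCR-corrected ACPR in Cohorts 1 and 2, so using it for the Run-in Cohort is an assumption, as are all other rates shown.

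**What to change.** In SAP 2.5.4.1 and 2.7.2.2, replace the z-interval as follows.

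- **Per arm.** Wilson limits (l, u) at the Kaplan-Meier estimate S, with effective n = S(1−S)/Greenwood variance. With 40 patients, 6 of them censored and one event at Day 29, S = 0.9714 and SE = 0.02816 give n = 35. That ratio is 0/0 without events, so there use the number still at risk just before the analysis day (Day 29, or Day 43). With 35 at risk the lower limit is 35/(35 + 3.84) = 90.1%.
- **Difference d within a cohort (MOVER).** Lower limit d − √((S_k−l_k)² + (u_c−S_c)²); upper limit d + √((u_k−S_k)² + (S_c−l_c)²).
- **Cohorts 1 and 2 pooled.** Weight each cohort's difference by w proportional to n_k·n_c/(n_k+n_c), scaled to sum to 1. Build the limits from the cohort limits L and U, not from Greenwood standard errors: lower limit Σwd − √Σw²(d−L)², and the upper limit likewise with (U−d).
- **SAP Section 4.** Record the change; the section now lists no departures from the protocol.

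The cost is SAP wording, a short macro, a declared departure from Protocol 12.4.4, and wider intervals. For example, with no failures at all, weights 35/55 and 20/55 give a pooled half-width of √((0.636×5.2)² + (0.364×8.8)²) ≈ 4.6 points, against 3.4 for a single Wilson-type interval at 110 per arm and zero as planned.

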2.6 Analysis of the key secondary objective

There is no key secondary objective in this study.

2.7 Analysis of secondary efficacy objective(s)

2.7.1 Secondary efficacy endpoints

Secondary efficacy variables include:

1. PCR-corrected ACPR at Days 15, Day 29 (Run-in Cohort) and 43;
2. Uncorrected ACPR at Days 15, 29, and 43;
3. Proportion of patients with parasitaemia at 12, 24, and 48 hours after treatment;
4. Time to parasite clearance (PCT), defined as time from the first dose until the first total and continued disappearance of (*P. Falciparum*) asexual parasite forms which remained at least a further 48 hours;
5. Time to fever clearance (FCT), defined as time from the first dose until the first time the body temperature decreased below and remained below 37.5°C (axillary equivalent) for at least a further 24 hours;
6. Proportion of patients with early treatment failure (ETF);
7. Proportion of patients with late clinical failure (LCF);
8. Proportion of patients with late parasitological failure (LPF);
9. Incidence rate of recrudescence and new infection at Days 15, 29 and 43.

Analyses of ACPRs (PCR corrected or uncorrected) will be based on the FAS and PPS. Analyses of other secondary efficacy variables will be based on the FAS.

2.7.2 Statistical hypothesis, model, and method of analysis

There are no pre-specified hypotheses for secondary endpoints. Model, method of analysis, and handling of missing values/censoring/discontinuations are presented in the following subsections by topic. There is no adjustment for multiplicity since these endpoints are supportive in this study.

2.7.2.1 PCR-corrected ACPR and uncorrected ACPR

Analysis will be performed on PPS and FAS.

If Cohort 2 does not stop early-

At each visit, the ACPR rate with 95% confidence intervals will be provided using Clopper-Pearson method for each treatment group by cohort. Two-sided 95% CI for the difference between two treatment groups will be provided using Wilson's uncorrected method by cohort. Two-sided 95% CI for the difference between two treatment groups will be provided for Cohorts 1 and 2 pooled using Mantel-Haenszel estimate of the common risk difference stratified by cohort (see SAS manual version 13.2 Pages 2681-2682, 2014).

If Cohort 2 stops early –

At each visit, the ACPR rate with 95% CIs will be provided using Clopper-Pearson method for each treatment group for Cohort 1 and 95% CIs for the Cohort 2; two-sided 95% CI for the difference between two treatment groups will be provided for Cohort 1 only using Wilson's uncorrected method. Handling of missing values/censoring/discontinuations

Data will be handled as follows for ACPRs (PCR corrected or uncorrected):

- For PCR-corrected ACPR, presence of parasitaemia which were determined to be new infection from Day 8 and before Day 29 are excluded from the PPS, however, new infections at Day 29 or after Day 29 but before Day 43 are included in the PPS. At Day 43, 2 analyses will be performed, these new infections are considered as non-responders in one analysis and as responders in another analysis. For FAS, similar 2 analyses will be performed, new infections prior to a visit will be considered non-responders in one analysis and as responders in another analysis.
- For the PCR-corrected ACPR, the patient who is not classified as PCR-corrected nonresponder at earlier timepoint, and the PCR data is missing will be excluded from the PPS based analysis; however, for FAS, the patient will be considered as non-responder from the day of test.
- New infection at a visit means no recrudescence at prior visits (e.g., new infection at Day 43 means no recrudescence).
- Missing/undetermined responses at a visit due to missing blood smear data at the visit will be counted as non-responders (PCR corrected or uncorrected) unless there is a later blood smear test indicating no parasitemia, for the FAS; however, such patients will be excluded from the PPS based analysis.
- Patients who received non-rescue anti-malarial medication before Day 29 will be excluded from the PPS; however, for the FAS, they will be considered in the analysis as if they had not taken the antimalarial drug. Note- Patients who take non-study anti-malarial medication due to repeated vomiting of study medication should be considered as treatment failure.

In addition, PCR-corrected and uncorrected ACPR rate will be calculated and plotted using the Kaplan-Meier method for each treatment group in the FAS and PPS (see [Section 2.5.4](#) and [Section 2.7.2.2](#)).

